The Immediate Extent of the Hypoalgesic Effect Following Central

Mobilisations to L3, L4 and L5.

October 27th 2023

Study Protocol

Study Design

The design of the study was a randomised, single-blind, repeated measures, cross-over design, performed in a single-centre environment. Ethical approval was gained from the School of Sport and Exercise Science ethics committee at the University of Worcester (ISES2018RF1). Informed consent was gained from each participant before testing.

Sample and Inclusion Criteria

The study included twenty asymptomatic participants (11 females and 9 males); the mean age of the participants was 21.9 years (±2.67, range 20- 30). A health questionnaire (based on the PARQ) was completed by each participant to establish any contraindications they may have to the experimental procedures, namely the application of vertebral mobilisations. No participants were required to be excluded as none of them had consulted their doctor in the last six months, were taking any medication, had an infection in the past two weeks, had no heart, asthma, diabetes, bronchitis, epilepsy or blood pressure issues, had any current muscle or joint injury, were able to train/exercise normally or knew of any other reason that would preclude them from participating.

Data Collection

Each participant was randomly assigned using a random number generator to the order in which their lumbar vertebral levels were mobilised and to the order of each dermatome level tested for the baseline and all three mobilisation interventions.

Before initiating the experimental procedure, the participant's age, height, and weight were recorded. The participant was instructed to lay on their back, on the plinth and had the five locations for dermatome testing marked with a water-soluble pen. The researchers utilised the method of using participant's finger breadth to establish dermatome testing sites (Gross et al 2015) the dermatome testing sites were based on Keegan and Garrett's dermatome map (Keegan & Garrett, 1948) see Figure 1. From this point forth, the spinal levels will be referred to as L2 or L3, respectively and the corresponding dermatome of the vertebral level will be referred to as DL2 or DL3.

Figure not included due to copyright reasons.

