Figure 1. The dermatome map was established originally by Keegan & Garrett (1948). DL2 landmark-4 participant's finger breadth inferior from ASIS, mid anterior thigh. DL3 landmark-8 participant's finger breadth inferior from DL2 landmark, mid anterior thigh. DL4 landmark- 2 participant's finger breadth superior from the proximal border of the patella, mid-way. DL5 landmark- 4 participant's finger breadth inferior from tibial tuberosity, then 1 participant's finger breadth lateral (so that the landmark is on the tibialis anterior, not tibia). S1 landmark- 1 participant's finger breadth inferior to the lateral malleolus. Adapted and used with permission from Anatomical Record. 1948;102(4):409.

Once these locations were marked on the participant's left leg, a demonstration of the Neuropen® (Owen Mumford, Oxfordshire, UK) was performed on the participant's hand (opposite to the side being tested). Once all this had been completed, baseline measures were taken. Using the Neuropen®, a standardised force of 40g was applied to one of the locations. The participant then received a small piece of card with a vertical 10cm visual analogue scale (VAS) line on it and a pen and was asked to "draw a horizontal line on the scale to indicate how much sensation you feel, 0 being can-not feel anything and 10 being an extremely strong sensation". Following this explanation, the participant was asked if they understood and whether they needed further instruction to complete the VAS card. Once the participant marked the card, the card and pen were collected and stored, this process was repeated with the remaining four locations (these five cards provided the baseline data). A new tip was used for each participant, and a decrease in PPS represents a reduction in pain.

Once baseline measurements were collected by the lead researcher, the participant was asked to turn onto their front; the first (pre-determined) lumbar vertebra was found using the iliac crest as an anatomical landmark for the differentiation test. When the correct vertebra was located, the experimenter pressed record on the laptop connected to the PGD plinth (see Cooper et al (2018) for full details) to record the force applied and calculate the frequency.

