The lumbar vertebra was mobilised using Maitland's vertebral mobilisation method for posterioranterior central vertebral pressures (PACVPs) for four sets of 30 seconds (Pentelka et al 2012) with up to 30s between each, at a grade III amplitude (Maitland et al 2005) and a target rate of 3Hz (Piekarz & Perry 2015) to ensure the total time for testing was less than fifteen minutes in duration, before the opioid system is activated (Beatti et al 2010). Once the fourth 30-second mobilisation had been completed, the researcher pressed stop on the laptop and asked the participant to roll onto their back. Then the next five sets of data were collected following the same procedure implemented for the baseline measures (collected in a different, pre-determined order each time). This process was repeated for the remaining two vertebrae.

Statistical Analysis Plan

A Multivariate Analysis of Variance (MANOVA) for individual levels against baseline and a One-way Analysis of Variance (ANOVA) for the collated (data set reduced to identify effects at either the same vertebral level as treated versus baseline, one, two or three above or below respectively) mobilisation effect including Tukey post hoc tests for both were conducted using IBM SPSS statistics 25, p values less than 0.05 were defined as acceptable. Effect sizes identifying Cohens d (Large 0.8, Medium 0.5, and Small 0.2) and Magnitude Based Inferences (MBI) were also calculated for each a more comprehensive analysis of the data.

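### The SAP plans a one-way ANOVA with Tukey tests for a repeated-measures cross-over, names no participant term, and does not say what value the collated analysis uses

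*Combined protocol and SAP*

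**What the plan says.** - **Design.** Study Design calls the trial a "randomised, single-blind, repeated measures, cross-over design". Sample and Inclusion Criteria gives 20 participants.
- **Measurements.** Data Collection has one baseline round at five sites (DL2, DL3, DL4, DL5, S1): "this process was repeated with the remaining four locations (these five cards provided the baseline data". Mobilisation starts only afterwards: "Once baseline measurements were collected by the lead researcher, the participant was asked to turn onto their front". Five more scores follow the mobilised vertebra, and "This process was repeated for the remaining two vertebrae".
- **Analysis.** The Statistical Analysis Plan names "A Multivariate Analysis of Variance (MANOVA) for individual levels against baseline and a One-way Analysis of Variance (ANOVA) for the collated" data. It describes the collation as "data set reduced to identify effects at either the same vertebral level as treated versus baseline, one, two or three above or below respectively". Tukey tests apply to both analyses: "mobilisation effect including Tukey post hoc tests for both were conducted using IBM SPSS statistics 25". The significance level is 0.05.
- **Not stated.** The SAP gives no participant, within-subject, order or period term. It does not say whether the collated value is the raw VAS score or a change from baseline, whether several scores per person in a category are averaged, or whether above and below are kept apart. It does not say whether the MANOVA was a repeated-measures one.

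**The concern.** A one-way ANOVA treats every value as coming from an independent unit. Here all values come from the same 20 people, each of whom appears in every category. The error term then mixes between-person and within-person variation, and the degrees of freedom count scores, not people.

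The title sets the question as "The Immediate Extent of the Hypoalgesic Effect Following Central" mobilisation, that is, how far from the treated level the effect reaches. The collated analysis addresses this most directly. If its sensitivity differs by distance for reasons unrelated to the effect, or if it contains no comparison with baseline, the pattern of significant and non-significant distances may not answer the question.

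**Working it through.** The plan gives no power calculation, SD or correlation, so it has no figure of its own to reproduce.

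**Layout (from Data Collection).** Three vertebrae (L3, L4, L5) and five sites give 5 + 3 × 5 = 20 scores per person, and 20 × 20 = 400 in all.

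| Category | Scores per person | Total |
|---|---|---|
| Baseline | 5 | 100 |
| Same level | 3 | 60 |
| One above / one below | 3 / 3 | 60 / 60 |
| Two above / two below | 2 / 2 | 40 / 40 |
| Three above / three below | 1 / 1 | 20 / 20 |

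Three above is only DL2 after L5, and three below is only S1 after L3. Baseline covers all five sites.

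**Simulation assumptions (not in the documents).** Total SD is 1. Six variance splits were used (participant / participant-by-site / participant-by-condition / residual): 0.7/0/0/0.3; 0.4/0.2/0/0.4; 0.5/0/0/0.5; 0.3/0.1/0.2/0.4; 0.2/0.1/0.3/0.4; 0.3/0/0.4/0.3. Ranges below run across these six.

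**(a) Raw scores, eight categories.** Error df = 400 − 8 = 392. The Tukey-Kramer critical |t| is 4.310/√2 = 3.047. The smallest significant difference from baseline is 3.047 × √(1/100 + 1/n):
- same level or one away (n = 60): 3.047 × 0.163 = 0.50 SD
- two away (n = 40): 3.047 × 0.187 = 0.57 SD
- three away (n = 20): 3.047 × 0.245 = 0.75 SD

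With no effect and no site differences, the omnibus test rejects in 0% to 3.4% of runs, so it is conservative. With a true 0.5 SD fall at every site, detection is 51% to 55% (same, one away), 31% to 38% (two) and 7% to 17% (three). When same level is significant, both three-away categories are non-significant in 53% to 81% of runs, against 12% to 40% with the contrasts proposed under the fix.

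Site differences can add false results. With no effect and an assumed gradient of −0.3 to +0.3 SD across sites, at least one distance-versus-baseline Tukey test is significant in 0.9% to 15.4% of runs. It exceeds 5% only in the three splits with participant-by-condition variance. At −0.15 to +0.15 SD the range is 0% to 5.4%.

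**(a′) Raw scores, above and below pooled.** The five categories hold 100, 60, 120, 80 and 40 scores. Error df = 395 and the critical |t| is 3.876/√2 = 2.740. The thresholds are:
- same: 2.740 × 0.163 = 0.45 SD
- one away: 2.740 × 0.135 = 0.37 SD
- two away: 2.740 × 0.150 = 0.41 SD
- three away: 2.740 × 0.187 = 0.51 SD

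Detection of a uniform 0.5 SD fall is 61% to 73%, 77% to 95%, 68% to 85% and 48% to 50%.

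**(b) Participant means.** There are 8 × 20 = 160 values and 152 error df, with between-person variance left in the error. Power for a 0.5 SD same-level effect is 0.2% to 7%, against 38% to 97% with the proposed contrasts.

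**(c) Same-site changes.** Site differences cancel, but only seven change categories remain and none is baseline. The omnibus test rejects in about 0.3% to 3% of runs with no effect, and in 0.2% to 3% with a true 0.5 SD fall everywhere.

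**Per-dermatome analysis, only if run as independent groups** (n = 20, four conditions). Power of one Tukey contrast at 0.5 SD is about 11–12%, 9%, 5–6% and 3–4% at assumed correlations 0.3, 0.5, 0.7 and 0.8. With a participant term it is 23%, 35%, 60% and 81%.

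**Proposed contrasts (19 df).** Without time drift, Holm family-wise error is 3.4% to 5.0%. Power for a uniform 0.5 SD fall is 43% to 99% (same), 36% to 94% (two) and 26% to 74% (three). With an assumed drift of 0.15 SD per round and no mobilisation effect, at least one Holm-adjusted contrast is significant in about 24% to 90% of runs. For the planned raw-score Tukey tests versus baseline the figure is about 9% to 29%. At 0.05 SD per round the figures are about 6% to 17% and 0% to 5%.

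**The case against.** **The wording may be shorthand.** One-way ANOVA could mean a one-way repeated-measures ANOVA, and the MANOVA could be a multivariate repeated-measures test. That is possible, but the SAP does not say so. The point is therefore about the plan as written, and the value analysed would still need stating.

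**The collated analysis is defined.** This stands in part. The SAP lists the distance categories, so a reader should not conclude that the grouping is missing. What is missing is the value, the rule for combining scores and whether above and below are pooled.

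**Four stronger readings are tempting, and the documents do not support them.**
- *The mismatch inflates false positives.* With participant clustering alone the raw-score test is conservative. Inflation needs site differences or time drift, neither of which the documents quantify.
- *The plan makes the effect look local.* A threshold that rises with distance needs eight raw-score categories, and even there same level and one away share 0.50 SD. With pooling, same level has a higher threshold than one or two away, though three away remains the hardest to detect.
- *With change scores, a uniform effect cannot be seen.* That is true of the collated ANOVA and its Tukey tests only. The SAP also plans a MANOVA against baseline, with effect sizes and magnitude-based inferences, where it might appear.
- *The missing participant term causes all the unequal precision.* Part of it comes from having one score per person at three away, and it remains under any analysis.

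**The remedy is not uniformly better.** This stands. In two of the six variance splits its power for same level is 48% and 43%, against 51% for the planned test, and under drift it rejects falsely more often.

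**Conclusion.** The point holds: as written, the analysis does not match the declared design, and the collated value is not specified. Nothing elsewhere in the document repairs this, and each interpretation has its own defect. With eight raw-score categories, sensitivity falls with distance (0.50 to 0.75 SD) and site differences are mixed into distance. With participant means, power for a 0.5 SD same-level effect is at most about 7%. With change scores, no distance is compared with baseline in the collated tests.

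The layout, degrees of freedom and thresholds follow from the protocol's counts, given the assumed interpretation of the SAP. All rejection rates and powers rest on assumed variances and are illustrative. Confidence is high for the mismatch and moderate to low for the size and direction of its effect on the results. Because the plan leaves open which analysis was run, the distance findings should not be relied on until it is stated and, where needed, redone.

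**What to change.** 1. **State the outcome** as change from the same site's own baseline, within each participant.
2. **Replace the one-way ANOVA and Tukey tests with seven participant-level contrasts**, averaging the listed site/vertebra changes within each person:
   - same: DL3/L3, DL4/L4, DL5/L5
   - one above: DL2/L3, DL3/L4, DL4/L5
   - two above: DL2/L4, DL3/L5
   - three above: DL2/L5
   - one below: DL4/L3, DL5/L4, S1/L5
   - two below: DL5/L3, S1/L4
   - three below: S1/L3

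   Test each against zero with 19 df and Holm adjustment, and report all seven with 95% CIs. Support any claim that the effect fades with distance by a direct within-participant contrast between distances, not by one being significant and another not.
3. **Per-dermatome analysis.** If it was run as independent groups, replace it with a repeated-measures analysis with paired, adjusted level-versus-baseline contrasts. If the MANOVA was repeated-measures, say so.
4. **Sensitivity analysis.** Fit a mixed model with participant, participant-by-site and participant-by-condition random effects and a centred mobilisation-order term (zero at baseline), if it converges.
5. **State the limits, with their size.** Baseline always comes first, so level-versus-baseline contrasts cannot be separated from time, and the drift figures above should accompany them. They show change since baseline, not a proven mobilisation effect. Three above and three below are one site each, so distance there cannot be separated from how that site responds, and power is lowest. In some variance splits the new same-level contrast has slightly less power than the planned test.
6. **Label the work a post hoc re-analysis**, since the SAP reports the analyses as already done.

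Cost: revised SAP wording and a re-run on data already collected, with no new participants or procedures.

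### Effects are defined against a single baseline taken before any prone lying or spinal contact, so a uniform response to handling cannot be told from mobilisation hypoalgesia and may look segmental

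*Combined protocol and SAP*

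**What the plan says.** Under Data Collection, the participant lies supine: "The participant was instructed to lay on their back, on the plinth and had the five locations for dermatome testing marked". The test pen is then demonstrated on the hand, and the five baseline readings follow: "Once all this had been completed, baseline measures were taken". Only afterwards does the participant go prone: "Once baseline measurements were collected by the lead researcher, the participant was asked to turn onto their front". The vertebra is located and mobilised in four 30-second sets with gaps of up to 30 seconds. Then "the researcher pressed stop on the laptop and asked the participant to roll onto their back", and the five sites are tested again. The cycle is repeated for the other two vertebrae, with no new baseline.

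Randomisation covers "the order in which their lumbar vertebral levels were mobilised" and the order of dermatome testing. Baseline has no place in the randomised sequence of conditions; it always comes first. No sham, prone-rest or contact-only period is described.

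The Statistical Analysis Plan names two analyses. The first is "A Multivariate Analysis of Variance (MANOVA) for individual levels against baseline". The second is a one-way ANOVA on collated data, grouped as "same vertebral level as treated versus baseline, one, two or three above or below respectively". Tukey post hoc tests are planned for both, with a 0.05 threshold.

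**The concern.** Every post-mobilisation reading differs from baseline in more than mobilisation. It follows a turn to prone, a period prone, palpation and pressure on the spine, a turn back, and the participant's awareness of having been treated. The outcome is a self-marked sensation score, so a response to expectation or handling is plausible. In a contrast with baseline, such a response counts in full as mobilisation effect. This would be so even with a single mobilisation and no drift over time.

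The title asks about the extent of the effect. If the non-specific fall were the same at every site, a correct analysis of extent should show no gradient. The collated categories pool different numbers of readings, however, so their precision differs. A uniform fall may reach significance at or next to the treated level and miss it three levels away. A reader who compares significant with non-significant categories would then see an effect fading with distance where none exists.

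**Working it through.** The plan gives no effect size, SD or power figure, so there is nothing of its own to reproduce.

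**Inputs from the documents:** 20 participants; levels L3, L4, L5; sites DL2, DL3, DL4, DL5, S1; alpha 0.05 (taken as two-sided; the plan does not say).
**Assumed:** uniform fall δ = 0.3 or 0.5 SD of the single-site change score; correlation ρ between a person's change scores of 0 or 0.5; no true mobilisation effect.

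**Step 1: cells per distance category.**

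| Mobilised | DL2 | DL3 | DL4 | DL5 | S1 |
|---|---|---|---|---|---|
| L3 | 1 above | same | 1 below | 2 below | 3 below |
| L4 | 2 above | 1 above | same | 1 below | 2 below |
| L5 | 3 above | 2 above | 1 above | same | 1 below |

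Same, one above and one below have 3 cells each; two above and two below have 2 each; three above and three below have 1 each. Total 3×3 + 2×2 + 2×1 = 15. Three above is DL2 only and three below is S1 only, so distance is partly confounded with site.

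**Step 2: chance that a uniform fall is significant against baseline (paired test).** The mean of k change scores has variance (1 + (k−1)ρ)/k. The standardised shift is d_z = δ·√(k/(1 + (k−1)ρ)), the noncentrality is λ = d_z·√20, and the critical value is t(0.975, 19 df) = 2.093.

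Example: δ = 0.3, k = 3, ρ = 0 gives d_z = 0.3×√3 = 0.520, λ = 0.520×4.472 = 2.32, and a probability of 60%. With ρ = 0.5, d_z = 0.3×√(3/2) = 0.367, λ = 1.64, and the probability is 34%.

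| δ | ρ | 3 cells | 2 cells | 1 cell |
|---|---|---|---|---|
| 0.3 | 0 | 60% | 44% | 25% |
| 0.3 | 0.5 | 34% | 31% | 25% |
| 0.5 | 0 | 96% | 85% | 56% |
| 0.5 | 0.5 | 74% | 69% | 56% |

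The gradient comes only from k. It shrinks as ρ rises and vanishes at ρ = 1.

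**Step 3: closer to the planned test.** A one-way ANOVA with Tukey was simulated with 8 groups: 100 baseline readings and 60, 40 or 20 readings per distance category, 400 in all; 2,000 runs per setting. The uniform shift d is here in SDs of a single reading, and within-person correlation of readings is 0 or 0.5. At d = 0.5, significance against baseline occurred in about 49–53% of runs at the same or adjacent level, 31–36% at two levels and 9–15% at three. At least one category was significant in about 85%. The misleading pattern (same or an adjacent level significant, neither three-level category significant) appeared in 13–23% of runs at d = 0.3, 53–63% at d = 0.5 and 17–19% at d = 0.8, where the far categories often reach significance too. Any difference between two distance categories was declared in about 0–4% of runs.

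**Step 4: can existing data supply a matched comparison?** Absolute distances seen at each site after L3, L4, L5 are: DL2 1, 2, 3; DL3 0, 1, 2; DL4 1, 0, 1; DL5 2, 1, 0; S1 3, 2, 1. Each site is seen at two or more distances and the sets overlap. With dermatome, period and absolute distance as terms, and all six orders of mobilisation represented, the fixed-effects design has 10 columns and rank 10. Distance is therefore estimable across all five dermatomes without using baseline.

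**The case against.** The strongest reply is that Tukey compares all pairs. If the MANOVA takes condition (baseline, L3, L4, L5) as its factor and the five dermatomes as outcomes, Tukey gives L3 v L4, L3 v L5 and L4 v L5 at each dermatome, and these are matched for handling. A reader might infer that the plan offers no matched comparison at all; the documents do not support that. What remains is that the plan does not say which contrasts will carry the claim of extent and words its effects against baseline. It specifies no participant term, so the crossover pairing is not used. In the collated ANOVA, distance-versus-distance comparisons also mix sites.

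A reader might also infer that baseline preceded all manual contact. It did not: the leg sites were marked and the pen was demonstrated on the hand beforehand. Only spinal contact and the turn to prone had not yet happened.

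Third, the gradient depends on correlation. A handling or expectation response would plausibly be shared across a person's sites, and at ρ = 0.5 the 0.3 SD gradient is only 34/31/25%. That stands, and it limits the claim of false extent. It does not touch the confounding in the baseline contrasts.

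Finally, a between-level contrast has its own faults: spread to adjacent levels and carry-over between consecutive mobilisations both pull it towards zero. That also stands, and it is why baseline contrasts should be kept alongside.

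**Conclusion.** The concern holds in this form: the baseline contrasts measure total response, specific plus non-specific, and cannot attribute it to mobilisation. That follows from the sequence of procedures and needs no assumption about size.

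The second part is conditional. Unequal pooling can make a uniform response look as if it fades with distance. The effect ranges from slight (34/31/25%) to marked (96/85/56%) over the assumed shifts of 0.3 to 0.5 SD and correlations of 0 to 0.5. Neither quantity is in the documents. It would be wrong to infer that a non-specific response did occur, or that any gradient found is an artefact; the documents report no outcome data. The point matters for the central inference, and the analysis remedy is cheap, so the plan should be changed.

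**What to change.** Amend the Statistical Analysis Plan as follows, using the data already collected.

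1. Base claims about segmental extent on within-participant, within-dermatome comparisons among the 15 post-mobilisation readings. One suitable form is a mixed model with participant (and participant-by-dermatome) random effects and fixed terms for dermatome, period and distance from the treated level (0, 1, 2, 3). Report the distance differences with confidence intervals. If above and below are to be kept apart, note that signed distance equals site index minus level index, so its linear trend is not estimable once dermatome and mobilised-level terms are both included.
2. Keep the baseline contrasts, but label them as total response and not as evidence of a vertebral-level effect. Do not infer extent from which distance categories are significant.

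The cost is SAP wording and a re-analysis. The price in inference is that an effect common to all levels cancels, adjacent spread shrinks the same-versus-adjacent difference, and carry-over can dilute the contrast. The two sets of results should therefore be read together. A handling-matched baseline is not proposed, because the twenty participants are reported as already tested.

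### The collated one-way ANOVA by distance ignores the repeated-measures structure, and the plan does not say which baseline scores each distance is compared with

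*Combined protocol and SAP*

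**What the plan says.** Study Design describes a "randomised, single-blind, repeated measures, cross-over design". Under Data Collection, five skin sites (DL2 to S1) are scored once before any mobilisation ("these five cards provided the baseline data"). After each of the three mobilisations (L3, L4, L5) the sites are scored again: "Then the next five sets of data were collected following the same procedure implemented for the baseline measures". Randomisation covers the order of the vertebrae and "the order of each dermatome level tested for the baseline and all three mobilisation interventions".

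The Statistical Analysis Plan names two analyses. One is "A Multivariate Analysis of Variance (MANOVA) for individual levels against baseline". The other is a one-way ANOVA on a collated "data set reduced to identify effects at either the same vertebral level as treated versus baseline, one, two or three above or below respectively", described as a "mobilisation effect including Tukey post hoc tests for both were conducted using IBM SPSS statistics 25".

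For the collated analysis the plan names no participant or site term. It does not say whether the outcome is the raw score or a change, or which baseline scores each distance is set against.

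**The concern.** The title asks about the extent of the effect, and the collated ANOVA is the only planned analysis by distance. If the five sites are the MANOVA's outcomes, which is not stated, that analysis compares each site with its own baseline but gives no estimate by distance.

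Two things are wrong with the collated analysis as written.

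- **Dependence.** A one-way ANOVA treats all scores as independent. Here every participant contributes to every distance and to baseline.
- **Undefined baseline comparison.** Distance from the treated vertebra largely determines which skin sites are in a group, from the anterior thigh at one end to the ankle at the other ("S1 landmark- 1 participant's finger breadth inferior to the lateral malleolus"). Whether ordinary differences in sensation between sites can pass for a distance effect depends on a choice that the plan leaves open.

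**Working it through.** The plan gives no error rate, power, site mean or SD for this analysis, so there is no figure to reproduce. All SDs and site differences below are assumptions. Unless stated otherwise, the SDs are 1.4 cm between participants, 0.8 cm participant-by-site and 1.2 cm residual, with n = 20 and no true effect.

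**1. Layout.** Number the sites DL2 = 1 to S1 = 5 and the vertebrae L3 = 2 to L5 = 4. Distance = site − vertebra.

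| Distance | Sites in the group | Scores | Mean site position | Minus mean of all five sites (3) |
|---|---|---|---|---|
| Three above | DL2 (after L5) | 20 | 1.0 | −2.0 |
| Two above | DL2, DL3 | 40 | 1.5 | −1.5 |
| One above | DL2, DL3, DL4 | 60 | 2.0 | −1.0 |
| Same level | DL3, DL4, DL5 | 60 | 3.0 | 0 |
| One below | DL4, DL5, S1 | 60 | 4.0 | +1.0 |
| Two below | DL5, S1 | 40 | 4.5 | +1.5 |
| Three below | S1 (after L3) | 20 | 5.0 | +2.0 |

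Over the 15 pairs, site has variance 2 and vertebra 2/3, so distance has variance 8/3. The correlation of distance with site is 2/√(2 × 8/3) = 0.87. Randomising the order does not change which site lies at which distance.

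**2. No participant term.**

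- *Raw scores, no site differences.* With 400 readings in 8 groups (Tukey critical |t| 3.047, 392 df), any false versus-baseline difference occurs in 0.02% of simulated trials. The error term carries 1.4² + 0.8² = 2.60 of a total variance of 4.04, most of which cancels within participants. The test is far too conservative.
- *Change scores.* A same-site change has residual variance 2 × 1.2² = 2.88. Let overall response vary between participants with SD τ and mean zero. The same-level mean (60 changes, three per participant) has true variance (2.88 + 3τ²)/60, but treating the changes as independent gives (2.88 + τ²)/60.
  - τ = 0.5: the true SE is √(3.63/3.13) = 1.077 times the assumed one. 1.96/1.077 = 1.82, a two-sided rate of about 7%.
  - τ = 1.0: √(5.88/3.88) = 1.231. 1.96/1.231 = 1.59, about 11%.
  - Simulation gives 7% and 11.5%.
  - τ = 0: this one test is at its nominal level. Tukey comparisons between distances on the same 300 changes still run at 2.2% to 2.7%, because distances share baseline cards.

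**3. Which baseline.** Three readings are open.

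- *Change from the same site's own baseline.* Additive site differences cancel.
- *Raw scores against baseline scores from the same sites.* Site means cancel too. Unpaired tests at a gradient of 0.75 cm per site gave false positives of 0.1% to 0.25% per distance and 1.1% for any. This is free of site bias but again too conservative.
- *Raw scores against baseline pooled over all five sites.* A gradient of g cm per site adds g times the last column of the table: up to 2g at three off, with opposite signs above and below.

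Rates of any false versus-baseline Tukey difference on the third reading:

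| Assumed SDs (cm) | g (cm per site) | Rate |
|---|---|---|
| 1.4, 0.8, 1.2 | 0.25 | 0.9% |
| 1.4, 0.8, 1.2 | 0.5 | 22% |
| 1.4, 0.8, 1.2 | 0.75 | 84% |
| 1.0, 0.5, 1.0 | 0.5 | 69% |
| 2.0, 1.0, 1.5 | 0.5 | 4.5% |

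A non-monotone 1 cm site pattern gave 0.5%.

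A true uniform reduction of 1 cm with g = 0.5 would have expected contrasts of −2.0, −1.75, −1.5, −1.0, −0.5, −0.25 and 0 cm from three above to three below. They are flagged in 91, 99, 98, 48, 1, 0 and 0% of trials, so a uniform effect would look one-sided.

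**4. The alternative.** Average each participant's same-site changes at each distance and test the seven means against zero with Holm. With no effect, any false positive occurs in 4.5% to 5.0% of trials in every gradient, SD and site-pattern setting above, and in 4.3% when overall response varies between participants. For the uniform 1 cm reduction the seven distances are flagged in 62, 88, 97, 97, 97, 88 and 62%.

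**5. Precision at three off.**

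- Same-site change: √(2.88/20) = 0.38 cm.
- Raw score minus pooled baseline, true sampling SE: √((0.64 × 0.8 + 1.44 × 1.2)/20) = √(2.24/20) = 0.335 cm.

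**The case against.** The strongest reply is that the text leans towards the harmless reading. What is collated is called a mobilisation effect and is set against baseline. Each site has its own baseline card, and the same sites are retested by the same procedure. A reader might infer from the layout that site differences have biased the distance results. The documents do not support that: no passage says that baseline is pooled over all five sites, and two of the three readings remove additive site differences. This part of the reply stands.

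The size is also wholly assumed. The severe figures need a pooled baseline, a steady thigh-to-ankle gradient and roughly 0.5 cm or more per site. That stands too.

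It could be said that one-way ANOVA is loose wording for a repeated-measures version. The plan uses the term repeated measures only for the design. A repeated-measures version would also need a rule for distances where a participant has two or three scores, and none is given. The reply does not remove the missing participant term, which affects all three readings.

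**Conclusion.** The point holds in two parts of unequal strength.

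- **Firm.** A one-way ANOVA without a participant term does not suit this design, and its error rates are not the nominal ones on any reading. The direction varies. It is far too conservative for raw scores without site differences. For same-level change it is too liberal (about 7% or 12%) if overall response varies between participants by an assumed SD of 0.5 or 1.0 cm.
- **Conditional.** Distance is tied to site by design, and the baseline comparison is undefined. Site differences enter the versus-baseline contrasts only with raw scores against a pooled baseline. Under the assumed values the harm is then anywhere from under 1% to about 84% false differences. The documents show an unspecified comparison, not a biased one.

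A reader might also expect the better analysis to be more precise. At three off it is not (0.38 against 0.335 cm). The gain is freedom from site bias and valid error rates. This should be fixed, and the data allow it.

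**What to change.** Replace the collated one-way ANOVA with a within-participant analysis:

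- Define the outcome as change from the same participant's baseline at the same dermatome site.
- Average it per participant at each distance, giving seven values.
- Test each mean against zero, with intervals and a multiplicity adjustment such as Holm.
- Compare distances within participant.

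State two limits. First, three above and three below each rest on one vertebra-site pair (20 values, against 60 at the same level). Second, because distance is site minus vertebra, the effects of the three on change cannot be fully separated (rank 12 of 13 parameters). For example, a response that differed by 0.5 cm per site would read as 0.5 × 2 = 1.0 cm at three off. A model with distance, site and vertebra together is optional.

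The cost is a minor re-analysis, since the plan reports the tests as already done, and more cautious wording at the outer distances. The SE at three off is slightly larger, as shown above. No new data are needed, because the five site-specific baseline cards per participant were collected.
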